##### **Stop Dates**

- If the year is unknown, then the date will not be imputed and will be assigned a missing value.
- If the month is unknown, then assign ‘December.’
- If the day is unknown, then assign the last day of the month.
- If the imputed date is after end of study date, then end of study date will be used.

#### **2.4.3. Handling of Missing Data in Efficacy Analysis**

For analysis of primary and secondary efficacy endpoints and other binary exploratory efficacy endpoints, missing endpoint data will be imputed using a nonresponder imputation (NRI) method, unless otherwise specified. Participants will be considered nonresponders for the NRI analysis if they have missing clinical efficacy data at a time point of interest.

For continuous exploratory efficacy endpoints expressed as change from baseline at Week 12, the primary analysis will use the analysis of covariance (ANCOVA) model for comparing MORF-057 group with the placebo group. Participants who have missing baseline value or the value at Week 12 will be excluded from the analysis. The details are described in Section [4.8.3](#).

### **2.5. Coding Dictionary for Adverse Event, Medical History and Medications**

All adverse events and medical history will be coded by system organ class (SOC) and preferred term (PT) using the most recent version of Medical Dictionary for Regulation Affairs (MedDRA) available at time of database lock.

The severity of adverse events will be graded by Terminology Criteria for Adverse Events (CTCAE 5.0 or later).

All medications will be coded using the most recent version of World Health Organization Drug Dictionary (WHODD) available at time of database lock.

## 2.6. Pooling of Study Centers

Unless otherwise specified, data from all study centers will be pooled for analysis.

## 2.7. Handling Rules for PK Concentration

### 2.7.1. Below limit of quantification (BLQ)

- BLQ at pre-dose will be set to zero for the calculation of the mean concentration for Visit 2 (Day 1 only). BLQs at pre-dose for all other subsequent dosing days or before the last quantifiable measurement will be imputed as lower limit of quantification (LLOQ).
- Mean concentrations at any individual time point will only be calculated if at least half of the participants have valid values (i.e., quantifiable, and not missing) at this time point.
- In cases where a mean value is not calculated, due to the above criterion not being met, the mean value will be set to missing.

### 2.7.2. Other Handling Rules

- Previous Evening Dose:
  - For participants who are randomized to Group 1 (200 mg BID for Induction Period and 100 mg BID for Maintenance/Extension Periods) and Group 2 (100 mg BID for both Induction and Maintenance/Extension Periods), if the previous evening dose was not taken, the pre-AM dose PK sample collected at the PK visit (except at visit 2) is considered invalid. However, all post-dosing PK samples remain valid.
- Morning dosing time:
  - If morning dosing time is not reported, then all pre-AM dose and post-dosing PK samples are invalid.
  - If morning dosing time is available, and any post-dose PK samples are collected more than 30 minutes outside the specified timepoint (i.e., PK sample collection time relative to morning dose > 30 mins), then the post-dose PK samples collected at that timepoint are considered invalid. For instance, for PK sample at 1hr after the AM dose, if the actual sample collection time relative to the AM dose is outside the window of 1hr ( $\pm$  30min), this PK sample will be considered as invalid.
- At Visit 5 (Week 12), if participants deviate from the protocol and start their maintenance treatment before completing the collection of all PK samples, the following rules will be used to handle the PK samples at this visit:
  - For participants randomized to Group 1 (200 mg BID for the Induction Period and 100 mg BID for the Maintenance/Extension Periods), any PK samples collected after the first

maintenance dose will be considered invalid. However, PK samples collected before the first maintenance dose remain valid.

- For participants randomized to Group 2 (100 mg BID for both Induction and Maintenance/Extension Periods) or Group 3 (100 mg QD-M for both Induction and Maintenance/Extension Periods), all PK samples will be considered valid, regardless of whether they are collected before or after the first maintenance dose.

All PK samples considered invalid and PK samples collected at early termination End of Treatment (EOT) visit will not be included in the PK summary but provided in the listings.

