**Table 3: Study Dose Regimens**

	Induction Period (12 Weeks)	Maintenance Period (40 Weeks)/ Maintenance Extension Period (52 Weeks)
Group 1	MORF 057 (200 mg B.I.D.)	MORF 057 (100 mg B.I.D.)
Group 2	MORF 057 (100 mg B.I.D.)	MORF 057 (100 mg B.I.D.)
Group 3	MORF 057 (100 mg Q.D. M)	MORF 057 (100 mg Q.D. M)
Group 4	Placebo	MORF 057 (200 mg Q.D. E)

B.I.D.: twice a day; Q.D. E: once a day (evening); Q.D. M: once a day (morning).

A study schema is provided in [Figure 1](#).

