For participants initially randomized into the placebo group during the Induction Period and subsequently switched to MORF-057 treatment (i.e., 200 mg Q.D.-E) during the Maintenance Period, unless otherwise specified, only the data collected during the Maintenance Period will be used in the 52-week Treatment Period Analysis to evaluate the effect of MORF-057 200 mg Q.D.-E. The data will be presented in the treatment group denoted by 200 mg Q.D.-E.

The data for the 104-week Total Treatment Period Analysis (see Section 1.5.3) will be presented by treatment groups similar to the 52-week Treatment Period Analysis described above, unless otherwise specified. All data during the 104-week Total Treatment Period will be used in the analysis for participants initially randomized to an active MORF-057 treatment group, and only the data during the Maintenance and Extension Periods will be used for participants initially randomized to placebo and subsequently switched to MORF-057 for maintenance treatment.

Unless otherwise specified, only scheduled visits including re-allocated visits (EOT or unscheduled visits, as described in Section 2.3) will be included in all by-visit analyses of efficacy and safety data. For the group of participants initially randomized to placebo and subsequently switched to MORF-057 for maintenance treatment, only the visits after Visit 5 (week 12) will be included in the by-visit analyses for the 52-week Treatment Period Analysis and the 104-week Total Treatment Period Analysis.

Data that are not summarized will be listed only. All data will be listed as collected for all randomized participants and will be ordered by randomized treatment group and visit if applicable.

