#### 4.10. Pharmacokinetic Analysis

Plasma concentrations of MORF-057 will be summarized by treatment groups at scheduled visit and time using descriptive statistics including number of participants, mean with SD, median, CV% and geometric mean with CV% based on PK Population.

Mean concentrations at any individual time point will only be calculated if at least half of the participants have valid values (i.e., quantifiable, and not missing) at this time point. In cases where a mean value is not calculated, due to the above criterion not being met, the mean value will be set to missing.

The handling rules for values below limit of quantification (BLQ) are described in Section 2.7.1.

The PK analyses for the Induction Period will include the PK data collected during the 12-week Induction Period, see Section 1.5.1. The PK analyses for the 52-week Treatment Period will include the PK data collected during the 52-week Treatment Period, see Section 1.5.2. Additional PK and PK/PD analyses will be conducted as deemed appropriate and may be reported separately from the Clinical Study Report.

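### Section 2.7.2 does not extend its missed-evening-dose rule to Group 4, whose only active maintenance dose is the evening one, so off-dose samples stay in the 200 mg Q.D.-E PK summary

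*SAP*

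**What the plan says.** Section 2.7.2 of the SAP sets three validity rules that matter here.

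- **Previous evening dose.** The rule opens with its scope: "For participants who are randomized to Group 1 (200 mg BID for Induction Period and 100 mg BID for Maintenance/Extension Periods) and Group 2". For these groups, "if the previous evening dose was not taken, the pre-AM dose PK sample collected at the PK visit (except at visit 2) is considered invalid". Samples after the morning dose are kept. Group 4 is not named.
- **Morning dosing time.** "If morning dosing time is not reported, then all pre-AM dose and post-dosing PK samples are invalid". This rule has no group limit.
- **Post-dose window.** If a sample is taken more than 30 minutes from its timepoint relative to the morning dose, "then the post-dose PK samples collected at that timepoint are considered invalid". This rule also has no group limit.

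The consequence of an invalid flag is stated at the end of the section: "All PK samples considered invalid and PK samples collected at early termination End of Treatment (EOT) visit will not be included in the PK summary". Such samples are only listed.

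Table 3 gives Group 4's maintenance regimen as 200 mg once daily in the evening. Table 5 gives two MORF-057 capsules per day, and Table 8 shows one placebo morning bottle and two active evening bottles.

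Section 4.10 says "The PK analyses for the 52-week Treatment Period will include the PK data collected during the 52-week Treatment Period", with concentrations summarised by treatment group, scheduled visit and time. For participants who switch from placebo, Section 4 restricts the 52-week analysis to maintenance data and adds: "The data will be presented in the treatment group denoted by 200 mg Q.D.-E".

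**The concern.** The evening-dose rule rests on a sound principle. A pre-AM sample does not represent the regimen if the active dose due the evening before was not taken. The principle applies with most force to Group 4, because the evening dose is that group's only active dose of the day. Yet Group 4 is outside the rule.

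The companion clause, which keeps the samples taken after the morning dose, makes sense for Groups 1 and 2 because an active morning dose follows the missed one. For Group 4 nothing active follows until the next evening, so every sample at that visit reflects the missed dose.

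The morning-time rule errs the other way. For a group with an active morning dose, a missing time leaves it unclear whether a nominal pre-dose sample really preceded the dose. For Group 4 in maintenance the morning capsule is placebo, so its missing time says nothing about the concentration in the pre-AM sample, and the sample is dropped without cause.

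At stake is the description of exposure under 200 mg Q.D.-E.

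**Working it through.** There is no figure in the SAP to reproduce. The check sets the rules against the dosing tables and then illustrates the size.

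**Step 1: does Section 2.7.2 reach maintenance?** Yes. The evening rule cites the maintenance and extension regimens of Groups 1 and 2, and Section 4.10 plans a 52-week PK summary.

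**Step 2: rules against active capsules in maintenance (Tables 5 and 8).**

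| Group | Active AM | Active PM | Evening rule applies | Morning-time rule applies |
|---|---|---|---|---|
| 1 | 1 | 1 | yes | yes |
| 2 | 1 | 1 | yes | yes |
| 3 | 1 | 0 | no | yes |
| 4 | 0 | 2 | **no** | **yes** |

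For Groups 1 to 3 each rule applies exactly where the corresponding dose is active. Group 4 is the only group where both are mismatched.

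**Step 3: effect on one sample.** Assumptions, none of them given in the SAP: mono-exponential decay, 12 h between morning and evening doses, and half-life t of 6, 12 or 24 h. After a missed evening dose, a Group 4 pre-AM sample lies about 36 h rather than 12 h after the last active dose. The ratio to the intended value is 2^(−24/t):

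- t = 6 h: 2^(−4) = 0.0625 (16-fold lower)
- t = 12 h: 2^(−2) = 0.25 (4-fold lower)
- t = 24 h: 2^(−1) = 0.50 (2-fold lower)

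The 24 h shift, and hence the ratio, is the same for later samples at that visit taken before the next evening dose.

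For Group 2 the shift is from 12 h to 24 h and the ratio is 2^(−12/t) = 0.25, 0.50 and 0.71. So the SAP excludes the smaller distortion and retains the larger one.

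**Step 4: effect on the Group 4 summary.** Let m be the fraction of summarised samples that follow a missed evening dose (assumed) and F the fold from Step 3.

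- Fall in geometric mean: 1 − F^(−m)
- Fall in arithmetic mean: m(1 − 1/F)

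| t | F | Geometric, m = 5% | Arithmetic, m = 5% | Geometric, m = 10% | Arithmetic, m = 10% |
|---|---|---|---|---|---|
| 6 h | 16 | 12.9% | 4.7% | 24.2% | 9.4% |
| 12 h | 4 | 6.7% | 3.8% | 12.9% | 7.5% |
| 24 h | 2 | 3.4% | 2.5% | 6.7% | 5.0% |

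Section 2.7.1 imputes pre-dose values below quantification after Day 1 as the LLOQ. That puts a floor under the largest falls, which the table ignores. The median, also reported under Section 4.10, would move little.

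**The case against.** The strongest objection is that the maintenance PK schedule is in the protocol, which is not at hand. The SAP does not say which Group 4 samples are taken in maintenance, or when relative to the morning capsule. This stands as a limit: affected samples cannot be counted. It does not remove the point, because Sections 4 and 4.10 plan a 52-week PK summary that includes 200 mg Q.D.-E, and Section 2.7.2 is the only rule set for its samples.

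Four stronger readings are tempting and are not supported.

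- **The ±30-minute window wrongly discards Group 4 samples.** Section 4.10 tabulates by scheduled visit and time, and Section 2.7.2 keys the post-dose timepoints to the morning dose. A sample well off its nominal time does not belong in that row for any group. Likewise, a post-AM sample with no morning time cannot be placed in a row. Only the loss of the pre-AM sample is clearly needless.
- **Section 2.8 shows how Section 2.7.2 should treat Group 4.** Section 2.8 concerns Visit 5 PD data collected after the first maintenance dose. It has no missed-dose rule for any group.
- **Group 3 has a matching gap**, because no rule checks its previous morning dose. Its exemption from the evening rule is coherent, since it has no active evening dose. A check of the previous morning dose would be a separate refinement, and the SAP does not show that this dose is recorded.
- **Group 4 validity should be judged by time since the evening dose.** Section 2.7.2 uses whether the evening dose was taken. It mentions no evening clock time.

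It is also fair that no hypothesis test, efficacy endpoint or safety analysis uses these flags.

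**Conclusion.** The point holds in a limited form. As written, Section 2.7.2 keeps Group 4 maintenance samples that its own principle would exclude, and drops Group 4 pre-AM samples because a placebo capsule's time is missing. With half-lives of 6 to 24 h and 5% of evening doses missed, the geometric mean for 200 mg Q.D.-E would be about 3% to 13% too low and the arithmetic mean about 2.5% to 5% too low, before any LLOQ floor. These are illustrations. Half-life, missed-dose rate, decay model and sampling schedule are all assumed.

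A reader might infer that the 52-week PK summary for this group is unreliable throughout, or that efficacy or dose-comparison conclusions are touched. The SAP supports neither. The effect is limited to the descriptive PK summary of one regimen and to any PK/PD work that reuses the flags, which Section 4.10 leaves open and may report separately. Severity: minor.

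**What to change.** Amend Section 2.7.2 for Group 4 at PK visits after Visit 5:

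1. If the previous evening dose was not taken, treat all PK samples at that visit as invalid for the summary and list them. State that the clause keeping later samples after a missed evening dose applies to Groups 1 and 2 only.
2. Do not invalidate a pre-AM sample solely because the morning capsule time is missing.
3. Leave the ±30-minute window for nominal post-AM timepoints unchanged.

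The cost is a few lines of text and one programming condition. The section already sets rules by randomised group and already uses taken/not-taken status for the evening dose. All participants take evening capsules under the blind (Sections 1.4.2 and 6.2), so that status should be available for Group 4 as well; confirm this against the CRF. Some Group 4 samples will leave the summary after missed doses, and some pre-AM samples will return to it. No dose or clinical procedure changes.

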### **1.5.1. Induction Period Analysis**

The Induction Period Analysis will be performed after all the participants have completed the Week 12 assessments or discontinued the study before the Week 12 assessments. The analysis will formally evaluate the primary and secondary efficacy endpoints, all the exploratory efficacy endpoints defined by Week 12, and safety of MORF057 vs placebo during the 12-week Induction Period. The PK and PD data during the 12-week Induction Period will also be summarized.

The 12-week Induction Period is defined as the time from the date of randomization to the Induction Period Last Dose date recorded on the Study Period Transition electronic case report form (eCRF) for participants continuing to the Maintenance Period, or the study end date (i.e., the date of the last visit including the SFU visit or last scheduled procedure) for participants who have discontinued the study before entering the Maintenance Period.

If participants continue to the Maintenance Period, they should complete all the Visit 5 (Week 12) assessments before starting their maintenance treatment according to the protocol. However, a small number of participants were observed to deviate from the protocol by starting their maintenance treatment shortly before completing all the Visit 5 (Week 12) assessments. In such cases, all efficacy assessments, clinical laboratory tests, vital signs and electrocardiogram (ECG) collected at Visit 5 (Week 12) will still be included in the analyses for the 12-week Induction Period, even if they are measured after the participants start their maintenance dose. The PK and PD samples collected at Visit 5 (Week 12) for these participants will be handled in the Induction Period Analysis according to the rules specified in Section 2.7 and Section 2.8. Any adverse events that occur after the date of last induction treatment dose will not be included in the Induction Period Analysis. If both the last induction treatment dose and the first maintenance treatment dose occur on the same day, any adverse events reported on that day will be considered for the Maintenance Period and not included in the Induction Period Analysis, unless there is evidence to confirm that the events occurred before the administration of the maintenance treatment.

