## 2.8. Handling Rules for PD Data

For  $\alpha 4\beta 7$  and  $\alpha 4\beta 1$  receptor occupancies, and relative CCR9 mRNA expression which are collected at Visit 5 (Week 12),

- If participants are randomized into Group 2 (MORF-057 100 mg B.I.D. – MORF-057 100 mg B.I.D) or Group 3 (MORF-057 100 mg Q.D.-M – MORF-057 100 mg Q.D.-M), all data collected at Visit 5 (Week 12) will be considered as valid and included in the table summary for the Induction Period analysis.
- If participants are randomized to Group 1 (MORF-057 200 mg B.I.D. – MORF-057 100 mg B.I.D.) or Group 4 (Placebo – MORF-057 200 mg Q.D.-E), any data collected after the first maintenance dose will be considered as invalid and not be included in the table summary but provided in the listings.

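### For Week 12 deviators in Groups 2 and 3, the SAP's PK validity rule has no exception for a nominal pre-AM sample drawn after that morning's maintenance dose

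*SAP*

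**What the plan says.** Section 1.5.1 reports that a small number of participants have already been seen to begin maintenance shortly before their Visit 5 assessments were finished. It refers their PK samples to section 2.7.2, where the rule applies "if participants deviate from the protocol and start their maintenance treatment before completing the collection of all PK samples".

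The rule then splits by group:

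- **Group 1**, whose dose changes at the switch: samples after the first maintenance dose are invalid. "However, PK samples collected before the first maintenance dose remain valid".
- **Groups 2 and 3**, whose dose is the same in both periods (Table 3): "all PK samples will be considered valid, regardless of whether they are collected before or after the first maintenance dose".

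Section 2.7.2 also has a 30-minute window. If a post-dose sample falls outside it, "then the post-dose PK samples collected at that timepoint are considered invalid". Invalid samples and those from an early-termination EOT visit are listed but not summarised. Section 4.10 summarises concentrations by treatment group at scheduled visit and time.

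**The concern.** The Group 2 and 3 rule turns on dose level: same dose before and after the switch, so the sample counts. That is sound for a sample scheduled after a dose. A sample scheduled before the morning dose also depends on timing. Once that morning's dose has been taken, the sample no longer measures a trough, whatever the dose level.

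Plasma concentration is the trial's stated PK endpoint and is shown by regimen in a dose-ranging study. A few post-dose values filed at the pre-dose time point could raise the apparent Week 12 trough in the two 100 mg arms. The corresponding Group 1 samples would be left out, so the arms would not be handled alike.

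**Working it through.** The SAP gives no figure to reproduce here. The check is textual, followed by an illustration of size.

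**Step 1: does any other rule in 2.7.2 catch the sample?** Take a Group 2 or 3 deviator who takes a maintenance dose in the morning and then gives the nominal pre-AM sample.

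- Previous-evening rule: concerns a missed evening dose, in Groups 1 and 2 only. It does not catch the sample.
- Unreported morning dosing time: invalidates pre-AM and post-dose samples, but only when the time is missing. It does not catch the sample when the time is recorded.
- 30-minute window: written for post-dose samples. It sets no condition on a pre-AM sample.
- Exclusion from the summary: invalid and early-termination EOT samples only.

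The sample therefore stays valid. Under section 4.10 it is summarised at its scheduled time, which is pre-dose. The same sequence in Group 1 gives a sample after the first maintenance dose, which is invalid.

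**Step 2: which deviators can be affected?** If maintenance began the evening before, the next pre-AM sample is still a proper trough. In Group 2 the evening maintenance dose is the same 100 mg. In Group 3 the evening maintenance bottles hold placebo only (Table 8). The problem needs a maintenance dose on the same morning, before the pre-AM draw.

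**Step 3: size, by assumption.** Let f be the share of a group's pre-dose samples that are misplaced, and R the ratio of a post-dose value to the trough. The SAP gives neither. If affected participants otherwise resemble the rest of their group:

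- arithmetic mean: (1 − f) + fR = 1 + f(R − 1), a rise of f(R − 1);
- geometric mean: a rise of R^f − 1.

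| f | R | Arithmetic mean | Geometric mean |
|---|---|---|---|
| 1% | 2 | +1.0% | +0.7% |
| 1% | 10 | +9.0% | +2.3% |
| 2% | 5 | +8.0% | +3.3% |
| 5% | 2 | +5.0% | +3.5% |
| 5% | 10 | +45.0% | +12.2% |

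With the planned 70 per group, one affected participant is 1/70 = 1.4% and three are 3/70 = 4.3%, so the range of f covers one to three people. If no affected sample is a nominal pre-AM sample, f = 0 and both rises are zero.

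**The case against.** The strongest reply is that the Visit 5 bullet answers only one question: does an early start of maintenance by itself invalidate a sample? For an unchanged dose the answer is no, and the other rules still apply. Three parts of this stand.

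- A reader might infer that the bullet overrides the 30-minute window. The natural reading is that the rules are cumulative. The same section says that post-dose samples stay valid after a missed evening dose, and nobody would take that to cancel the window.
- The step from valid to summarised as pre-dose is an inference. The SAP does not list the Week 12 PK time points, nor say whether a sample drawn after the dose keeps its pre-AM label. Summary by scheduled time makes this the literal result, but a careful programmer could do otherwise.
- Nothing shows that any pre-AM sample was affected. For a same-day switch, the capsule-count convention in section 4.6.2.2 assumes induction capsules in the morning and maintenance in the evening, which would leave that morning's pre-dose sample untouched.

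A reader might also infer that Group 1 is fully protected. It is not: its exclusion depends on the first maintenance dose. A Group 1 pre-AM sample drawn after a morning induction dose is caught by no explicit rule, at Week 12 or earlier.

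Finally, a reader might extend the point to receptor occupancy, because section 2.8 says of Groups 2 and 3 that "all data collected at Visit 5 (Week 12) will be considered as valid and included in the table summary for the Induction Period analysis". Occupancy is summarised by scheduled visit and the SAP defines no trough time point for it, so no label is shown to be breached.

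The reply does not remove the core. The bullet says all samples, without exception, and no stated rule invalidates a pre-AM sample drawn after the morning dose.

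**Conclusion.** The point holds in a narrow form. A stated rule, followed literally, files a post-dose concentration at the pre-dose time point for those Group 2 and 3 deviators who took a maintenance dose the same morning before the pre-AM draw. It excludes the same sample in Group 1. It does not reach other Group 2 and 3 participants.

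The size cannot be known from the SAP and may be zero. The 1% to 45% (arithmetic) and 0.7% to 12% (geometric) ranges rest wholly on the assumed share and ratio. The median, which section 4.10 also reports, is less sensitive to a few such values. A reader might infer a bias in the trial's conclusions. The SAP does not support that, because these PK summaries are descriptive and no efficacy test or safety summary uses them.

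**What to change.** Amend the Group 2 and 3 bullet in section 2.7.2 along these lines: samples collected after the first maintenance dose remain eligible because the dose is unchanged, subject to the other timing rules of this section, including the 30-minute window.

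Add one general rule for all arms and all PK visits after Visit 2: a pre-AM sample whose actual collection time is after that morning's dose is invalid for the pre-dose summary and is listed only. This also closes the Group 1 gap. Section 2.8 needs a matching condition only for a PD measure that has a defined pre-dose time point.

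The cost is two sentences and a small programming check on dosing and collection times that 2.7.2 already uses. The downside is a few fewer pre-dose values. With so few removed, the requirement that at least half of participants have valid values is unlikely to be at risk.
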